8.3.3 Safety Analyses

8.3.3.1 Adverse events

Safety will be assessed primarily by summarizing TEAEs, including treatment-emergent SAEs, and the proportion of subjects with TEAEs and treatment-emergent SAEs in each individual JBT-101 cohort (Cohort 1, Cohort 2, and Cohort 3) to the placebo (Cohort 4).

For placebo and each JBT-101 cohort, the frequency of AEs and SAEs from Screening through Visit 6 (Day 113) will be summarized by system organ class, preferred term, severity (grade), and relationship to study treatment.

Safety endpoint identified in Section 3.2.3, *Safety Endpoints*, will be summarized and listed separately. With the exception of the "psychotropic activity" endpoint, safety endpoints are "events". For each such endpoint, the number of events and numbers and percentages of subjects who experience these events will be summarized for placebo and each individual JBT-101 cohort. No formal statistical testing will be performed to compare safety in different cohorts.

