3.2.3 Safety Endpoints

Safety will be evaluated by describing incidence of treatment-emergent adverse events (TEAEs) from Visit 1 (Day 1) through 6. TEAEs will be identified by monitoring subject-reported AEs, vital signs, medical history, physical exams, blood and urine safety tests, 12-lead electrocardiograms, and the ARCI-M. Analyses on the following specific events are planned.

- 1. Any Grade 3 or higher AE or SAE that, in the opinion of the blinded site investigator, is at least possibly related to study product. Unless noted otherwise, grading is defined by the National Cancer Institute (NCI) Common Terminology Criteria for Adverse Events (CTCAE) system version 4.0.
- 2. QTc prolongation > 500 msec total duration and > 60 msec from Visit 1 (Day 1) QTc interval prior to study drug administration
- 3. Mild/moderate and severe disease flares by SELENA SLEDAI Flare Index
- 4. BILAG 2004 disease flares, defined as one new BILAG A or two new BILAG B scores
- 5. Aspartate aminotransferase (AST) or alanine aminotransferase (ALT) \ge 3 x upper limit of normal and total bilirubin > 1.5 x the upper limit of normal (confirmed on repeat testing)
- 6. Tolerability, assessed by incidence of discontinuation of study product due to TEAEs at least possibly related to study product from Visits 1 (Day 1) through 5 (Day 85)
- 7. Psychotropic activity, assessed using the ARCI-M

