6.4.1.1 Evaluation of Eligibility and Randomization

The subject's average of 7-day maximum daily pain NRS score will be computed by the IVRS and reported to site personnel.

If the average is \geq 4, and the subject meets other eligibility criteria for enrollment, then proceed as follows:

- Instruct the subject to continue to record maximum daily pain NRS score using the IVRS. Randomization will not be allowed, if compliance with reporting falls below 67% during the Screening period.
- Schedule Visit 1 (Day 1) (within 42 days of 1st Screening assessment)
 - Randomizations must occur at least 7 days prior to Visit 1 to ensure that drug will be available on site for Visit 1.
 - Instruct eligible subjects to hold short-acting analgesics for 6 hours and NSAIDs and long-acting analgesics for 12 hours prior to Visit 1 (Day 1).
- Randomize the subject (ensure sufficient time for shipment of study drug prior to the scheduled Visit 1 (Day 1))

If the subject is not eligible, inform the subject and let them know IVRS will no longer accept daily entries.

6.4.2 **Treatment Period**

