A. The screening period can be any duration between 7 and 42 days prior to Visit 1 (Day 1), provided the duration is adequate to ensure the subject meets all inclusion and exclusion criteria and drug can be shipped to the site on time for that subject. Screening can take place over more than one visit to the clinic. Screening laboratory tests, other than HIV, hepatitis, or pregnancy testing, can be repeated at the investigator's discretion.

- B. For women of childbearing potential.
- C. Seated (> 5 minutes) blood pressure and pulse.
- D. Will be measured at Visit 1 (Day 1) both before and 2.5 to 3.5 hours after administration of study product in the clinic.
- E. Record within 24 hours after most recent diary entry to prevent reporting of the same data.
- F. ARCI-M will be assessed at the Early Withdrawal Visit if a subject is withdrawn from the study or discontinues the study prior to Visit 6 (Day 113).
- G. At the end of treatment, both the subject and physician will complete a Treatment Satisfaction Survey. If a subject withdrawals from treatment prior to Day 85, the Treatment Satisfaction Survey will be completed at the Early Withdrawal Visit.
- H. Infectious disease screen including HIV antibody, hepatitis B surface antigen, hepatitis C virus (HCV) antibody with HCV RNA (PCR) if antibody positive (unless documented as negative within 12 weeks prior to the Screening visit).

- I. TB testing will be done centrally using a QuantiFERON® blood test. Testing is optional if skin or blood testing was done within 12 months before Visit 1 (Day 1), with documented negative results. See section 6.1.10 *Tuberculosis Screening* for repeat testing options.
- J. For women > 45 and ≤ 55 years of age with no menses for < 2 years.
- K. Complete metabolic panel includes at least glucose, urea nitrogen, creatinine, sodium, potassium, chloride, carbon dioxide, calcium, total protein, albumin, total bilirubin, alkaline phosphatase, aspartate aminotransferase, alanine aminotransferase, and calculated glomerular filtration rate.
- L. Blood and urine tests will be performed prior to study product administration.
- M. Laboratory tests as relevant to the reason for the unscheduled visit.
- N. Pregnancy test at screening can be done through a blood or urine test.
- O. If the subject provides written informed consent, blood samples, including serum, plasma, mRNA, and PBMC culture supernatants, will be stored for future unspecified studies related to JBT-101 or SLE.

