7.3 Collection and Recording of Adverse Events

7.3.1 **Collection Period**

AEs of Grade 2 and above will be collected from time of signing of informed consent until the subject completes study participation, or until 30 days after he/she prematurely withdraws (without withdrawing consent), or is withdrawn from the study. See Section 7.4, *Grading and Attribution of Adverse Events* for grading criteria.

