7.4 Grading and Attribution of Adverse Events

7.4.1 Grading Criteria

The study site will grade the severity of adverse events experienced by the study subjects according to the criteria set forth in the National Cancer Institute's Common Terminology Criteria for Adverse Events (CTCAE) version 4. This document (referred to herein as the NCI-CTCAE manual) provides a common language to describe levels of severity, to analyze and interpret data, and to articulate the clinical significance of all adverse events. The NCI-CTCAE has been reviewed by the Protocol Chairs and has been deemed appropriate for the subject population to be studied in this protocol.

Adverse events will be graded on a scale from 1 to 5 according to the following standards in the NCI-CTCAE manual:

- Grade 1 = mild adverse event.
- Grade 2 = moderate adverse event.
- Grade 3 = severe and undesirable adverse event.
- Grade 4 = life-threatening or disabling adverse event.
- Grade 5 = death.

For grading an abnormal value or result of a clinical or laboratory evaluation (including, but not limited to, a radiograph, an ultrasound, an electrocardiogram etc.), a treatment-emergent adverse event is defined as an increase in grade from baseline or from the last post-baseline value that doesn't meet grading criteria (i.e. Grade 0, normal). Similarly, changes from screening to baseline will also be recorded as adverse events, but these are not treatment-emergent. If a specific event or result from a given clinical or laboratory evaluation is not included in the NCI-CTCAE manual, then an abnormal result would be considered an adverse event if changes in therapy or monitoring are implemented as a result of the event/result. Grade 2 or higher AEs will be reported on the appropriate AE electronic case report (AE eCRF) for this study.

In addition, for this study, BILAG 2004 disease flares will be graded as follows:

- Mild SLE flare (Grade 1): New BILAG 2004 grade C in one or more organ systems
- Moderate SLE flare (Grade 2): New BILAG 2004 grade B in one or more organ systems
- Severe SLE flare (Grade 3): New BILAG 2004 grade A in one organ system
- Life-threatening or disabling SLE flare (Grade 4): A life-threatening or disabling new BILAG 2004 grade A

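### The only term-level adverse event table stated by cohort starts at Screening, so pre-dose events enter each arm's frequencies

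*Protocol*

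**What the plan says.** Section 3.2.3 of the protocol sets the safety window: "Safety will be evaluated by describing incidence of treatment-emergent adverse events (TEAEs) from Visit 1 (Day 1) through 6". Section 8.3.3.1 opens in line with that: "Safety will be assessed primarily by summarizing TEAEs, including treatment-emergent SAEs, and the proportion of subjects with TEAEs and treatment-emergent SAEs", each JBT-101 cohort being set against placebo.

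The next sentence of 8.3.3.1 covers placebo and each JBT-101 cohort and changes both the event type and the window: "the frequency of AEs and SAEs from Screening through Visit 6 (Day 113) will be summarized by system organ class". It goes on to name preferred term, grade and relationship to study treatment. No other sentence in 8.3.3.1 commits to a breakdown at that level.

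The data will contain pre-dose events. Section 7.3.1 says "AEs of Grade 2 and above will be collected from time of signing of informed consent", and Section 7.4.1, on abnormal clinical and laboratory results, says that "changes from screening to baseline will also be recorded as adverse events, but these are not treatment-emergent". Nothing in 8.3.3.1 takes such events out of the arm columns.

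**The concern.** Read literally, the primary summary gives treatment-emergent totals and proportions of subjects, while the table that shows which events occurred also counts events from before any subject took study product.

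Term level is where a specific drug effect would be looked for. Section 1.3.4 reports dizziness in 11%, fatigue in 10.2% and dry mouth in 5.6% of subjects given up to 60 mg per day. In an arm of about 25, 10% is two or three subjects, so one pre-dose event visibly changes a row. Those earlier percentages include mild events, whereas this trial collects only Grade 2 and above, so rows here may hold fewer still. No formal safety testing is planned, so readers will judge these tables by eye. Pre-dose events fall on all arms alike in expectation. They do not favour one arm, but they add noise and pull ratios against placebo towards 1.

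**Working it through.** The protocol states no figure for the adverse event tables, so there is nothing to reproduce. The check is the length of the pre-dose window and an illustration of its effect.

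**Inputs**
- Post-dose window: 84 days of treatment + 28 days of follow-up = 112 days (Section 3.1).
- Longest pre-dose window: 42 days (Section 6.4.1; Table 3, footnote A).
- Shortest pre-dose window: footnote A formally allows 7 days. However, Section 3.1 requires seven days of pain scores after the initial visit to establish eligibility, and Section 6.4.1.1 then says "Randomizations must occur at least 7 days prior to Visit 1". In practice 7 + 7 = about 14 days.
- Arm size: about 25 (Section 8.1).
- Background event rate: not given. Assumed constant and equal before dosing and on placebo.

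**Share of the counted window before the first dose**, S/(S + 112):
- S = 14: 14/126 = 11%
- S = 42: 42/154 = 27%
- (Formal minimum, S = 7: 7/119 = 5.9%)

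**Ratio of expected event counts**, with the rate doubled on drug for 84 days and equal to background otherwise, in units of background-rate days:

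| Window | Drug | Placebo | Ratio | Difference |
|---|---|---|---|---|
| Visit 1 to Visit 6 | 2×84 + 28 = 196 | 112 | 1.75 | 84 |
| plus 14 pre-dose days | 210 | 126 | 1.67 | 84 |
| plus 42 pre-dose days | 238 | 154 | 1.55 | 84 |

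The ratio shrinks; the difference in expected counts is 84 in every row.

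**Sensitivity to the assumed effect.** If the rate is instead doubled over all 112 days, the ratio of 2.0 becomes (2×112 + 14)/126 = 1.89 or (2×112 + 42)/154 = 1.73.

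**Proportions of subjects.** Let p0 and p1 be the placebo and drug proportions over 112 days. Adding S pre-dose days at the placebo rate gives q = 1 − (1 − p) × (1 − p0)^(S/112). With assumed values of 10% and 20%:
- S = 14: factor 0.9^0.125 = 0.987; 11.2% against 21.0%; risk ratio 1.88; difference 9.9 points.
- S = 42: factor 0.9^0.375 = 0.961; 13.5% against 23.1%; risk ratio 1.71; difference 9.6 points.

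The loss is larger for common rows. At 50% against 70% with 42 days, the table would show 61.4% against 76.9% (unrounded difference 15.4 points), so a 20-point difference shrinks by 4.6 points.

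**The case against.** A reader might infer that the safety comparison with placebo as a whole is diluted. The protocol does not support that. The sentence immediately before the Screening-based one restricts the primary comparison to treatment-emergent events, and 8.3.3.1 also says that the Section 3.2.3 endpoints are summarized separately. Possibly related Grade 3 or higher events, discontinuations for possibly related treatment-emergent events, and the ARCI-M scores before and after dosing (Section 8.3.3.4) do not pass through the affected table.

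A reader might also infer that pre-dose events are being attributed to study product. That is too strong. The table groups subjects by cohort and shows relationship as a separate split, so a correctly coded pre-dose event falls in the unrelated rows. One reservation remains: the relationship code in Table 4 covers study procedures as well as the product, so an event caused by a screening procedure could be coded as related.

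It can further be said that an all-event table is a normal supplement when collection starts at consent, that nothing forbids a term-level table of treatment-emergent events, and that Section 8.10 leaves detail to a statistical analysis plan that is not shown. This is fair, and it keeps the point small. It does not remove it: the Screening start is a window the protocol states, not a gap it leaves, and the term-level breakdown is tied in words only to that window.

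Finally, the absolute excess in expected counts is unchanged, the 1.55 figure needs every subject to use the full 42 days, and differences in proportions move little for uncommon terms. All of that stands.

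**Conclusion.** The point holds for one table. The by-cohort summary by system organ class, preferred term, grade and relationship counts all events from Screening, while Sections 3.2.3 and 7.4.1 and the opening of 8.3.3.1 work with treatment-emergent events. Ratios in that table are pulled moderately towards 1, by the amounts worked out above. Those sizes rest on an assumed constant background rate and an assumed doubling on drug; the direction needs only that some events occur before dosing and that the drug raises the rate afterwards. The effect is on the readability of a descriptive table in small arms. It does not bias the primary safety assessment, and the severity is minor.

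**What to change.** In Section 8.3.3.1, state that the tables by cohort for system organ class, preferred term, grade and relationship use treatment-emergent adverse events and treatment-emergent serious adverse events, meaning onset or worsening after the first dose through Visit 6. Put events between consent and first dose in a separate listing. An all-event table from Screening may stay as a supplement if labelled as such.

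This brings 8.3.3.1 into line with 3.2.3 and 7.4.1. It costs one sentence. Collection, visits and sample size do not change, and no new data are needed.

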8.3.3.2 Laboratory safety outcomes

Results of blood and urine laboratory safety tests, including CBC with cell differential and platelets, metabolic panel, and urine tests will be summarized by visit and time point using descriptive statistics for continuous measures. Changes from Visit 1 (Day 1) will also be summarized. Shift tables will be presented summarizing the shift from Visit 1 (Day 1) to subsequent visits. Results will be presented for placebo and each individual JBT-101 cohort.

8.3.3.3 Electrocardiograms and QT/QTc intervals

The QT/QTc intervals and change from Visit 1 (Day 1) to subsequent visits will be summarized by visit using continuous summary statistics for placebo and each individual JBT-101 cohort.

8.3.3.4 ARCI-M questionnaire

ARCI-M questionnaire scores will be summarized by visit for Visits 1 (Day 1) (before and after first dose of study drug), 3 (Day 29), and 5 (Day 85), and for change from Visit 1 (Day 1) prior to the first dose of study drug to the visit using continuous summary statistics. The number of subjects with an increase in score by ≥ 1 from Visit 1 (Day 1) prior to study product administration will be presented by visit for Visit 1 (Day 1) after study drug administration, Visits 3 (Day 29) and 5 (Day 85).

8.3.4 Plasma Concentrations of JBT-101 and Metabolites

Results of JBT-101 plasma concentrations and metabolites for Visits 1 (Day 1) and Visit 2 (Day 15) will be described, using continuous summary statistics, by visit.

In addition, plasma concentrations will be listed by subject and cohort in a blinded manner, using a mock identification number separate from the subject id, at several times during the trial to determine whether exposure to JBT-101 in the SLE subjects is within the expected

range for the doses administered. Complete analyses of the plasma concentrations and metabolites will be done at the end of the trial.

8.3.5 Mechanistic Analyses

Descriptive statistics and plots (including, but not limited to, those described subsequently) will be used to gain an understanding of the data prior to developing any statistical models. Means, medians, standard deviations, minimums, and maximums will be computed for each continuous mechanistic endpoint at each time point for treatment groups and separately for subjects who do/do not experience clinically significant disease reactivation. For dichotomous mechanistic endpoints, frequencies and percent's will be computed at each time point for treatment. To gain a better understanding of trends over time, summary statistics (e.g., means, medians, or percents) will be plotted versus time at the relevant time points. Plots for individual subjects may also be useful. Complete analyses of the mechanistic endpoints will be done at the end of the trial and will be described in a statistical analysis plan for mechanistic studies.

8.4 Interim Analysis

Interim analyses of data will be reported to the DSMB at planned DSMB meetings and as requested by the DSMB. Planned interim analyses for the DSMB will focus on study conduct and subject safety and may include information on enrollment, randomization, site activation status, major protocol deviations, subject status and demographics, and safety analyses. In addition, the DSMB may review selected efficacy data.

No other interim analyses are planned.

8.5 Other Statistical Considerations

8.6 Covariates

No specific adjustments for covariates are planned for this study.

8.7 Multi-center Studies

No special consideration of site effects is planned. The number of subjects at some study sites is expected to be insufficient (< 5 subjects) for evaluation of site effects. In addition, because the maximum daily pain NRS is patient-reported rather than physician-assessed, site effects would be expected to have a minimal impact on primary endpoint analysis.

8.8 Multiple Comparisons and Multiplicity

The primary analysis for the efficacy of JBT-101 compares the individual trajectories of the 4 cohorts over time. Section 8.3.2 describes the use of Dunnett's test for multiple comparisons against the placebo group. The secondary efficacy analyses will evaluate trends for efficacy, with p-values and confidence intervals presented as descriptive measures of strength of

evidence rather than formal statistical inference. Therefore, no additional multiplicity adjustments are needed for this study.

8.9 Examination of Subgroups

Exploratory subgroup analyses of efficacy endpoints will be done based on subject Screening 7-day average of the maximum daily pain NRS score ≤ 6 versus ≥ 7 and Fibromyalgia Symptom Scale score < 13 and ≥ 13 at Visit 1 (Day 1).

